3.2 Dosing

The initial group of 3 subjects will be treated with a 2-hour intravenous infusion of 100-mg/m²/day (Dose Level 1) liposomal annamycin daily for 3 consecutive days followed by 18 days off study drug (i.e., 1 treatment cycle = 21 days). Provided that no subject experiences a DLT (defined in [Section 3.4](#)) during the induction treatment cycle through Day 28, the ensuing group of 3 subjects will receive 120-mg/m²/day (Dose Level 2) liposomal annamycin.

The liposomal annamycin dose levels planned for investigation are outlined in [Table 3](#). The starting dose is Dose Level 1.

Table 3: Liposomal Annamycin Dose Levels

[figure not shown]
Dose Level Designation	Liposomal Annamycin Dose (mg/m ² /day) × 3 days
-1	90
1	100
2	120

For each dosing cohort, if 1 of the 3 initial subjects experiences a DLT ([Section 3.4](#)), the cohort of subjects at that dose level will be expanded to 6 subjects ([Figure 1](#)). If at least 2 of the 6 subjects experience a DLT, then 3 subjects will be treated at a lower dose. If a DLT occurs in at least 2 out of 6 subjects at Dose Level 1, the next 3 subjects will be enrolled into Dose Level -1. The MTD is defined as the highest dose of liposomal annamycin at which fewer than 2 (of a cohort of up to 6) subjects experience a DLT. The RP2D is defined as the dose to be

explored in the expansion phase portion of the study, based on the aggregate data of safety and efficacy.

Figure 1: Schematic of Dosing Plan

Liposomal annamycin will be administered for a single induction cycle.

Abbreviations: DLT = dose-limiting toxicity; HSCT = hematopoietic stem cell transplantation.

3.3 Safety Considerations

Subjects will be hospitalized for the full 3 days of liposomal annamycin administration. If a subject experiences a DLT as defined in [Section 3.4](#), or any severe or life-threatening event occurs at any time over the first 3 days, dosing should be stopped and the subject should be permanently discontinued from the study. In addition to the DLT criteria in [Section 3.4](#), the severe or life-threatening events include (but are not limited to) development of an anaphylactic reaction during or after the infusion, clinical or radiological evidence of left ventricular dysfunction with dyspnea and pulmonary rales, cardiomegaly or signs of pulmonary hypertension on chest x-ray, or acute cardiotoxicity ([Section 3.3.1](#)).

Additional criteria for safety evaluation after the initial dose during the induction cycle includes creatinine levels increasing to 1.5 times those of baseline or liver function tests increasing to 2 times those of baseline, in which case the next dose of the study drug will be decreased by 25%. If there is further deterioration of organ function after the next dose, the subject will be permanently discontinued from the trial. If these changes are acutely 2 or 3 times those of baseline, respectively, the study drug will be held, and subjects will be monitored for resolution of these changes. If there is prompt resolution (within 2 to 5 days), a rechallenge at a 25% lower dose will be attempted, and if any additional toxicity is observed, the subject will be permanently

discontinued from the trial. If resolution takes longer than 5 days, the subject will not be rechallenged and will be permanently discontinued from the trial.

Subjects successfully completing the first 3 days of dosing will then be evaluated weekly thereafter during the induction cycle of treatment (the induction cycle consists of 21 days [3 weeks total], with the first 3 consecutive days of daily liposomal annamycin treatment followed by 18 days off of liposomal annamycin).

3.3.1 Cardiotoxicity

Subjects will be evaluated before the start of liposomal annamycin treatment and during the first 3 days of liposomal annamycin treatment, with special consideration for potential cardiotoxicity based on documented literature ([Section 1.6](#)) that provides currently relevant recommendations. Since acute cardiotoxicity may occur immediately to weeks following treatment and can present as arrhythmias, ST and T wave abnormalities, pericarditis-myocarditis syndrome, and acute heart failure, the subject will be observed in the hospital with daily, diligent attention to evaluation of cardiac status, inasmuch as prompt therapy can provide substantial recovery ([Cardinale et al. 2015](#)). Guidelines for limiting the total cumulative dose of anthracyclines will be followed, as per an inclusion criterion that limits any subject with significant cumulative dosing due to prior regimens in addition to anticipated exposure to annamycin (See [Section 4](#) and [Appendix E](#)). Subjects will also have clinical and electrocardiographic examinations evaluated at the anticipated maximal plasma concentrations, and again weekly during the induction cycle of treatment with multiple-gated acquisition (MUGA) or echocardiogram (ECHO) scans or ECHO strain evaluations performed every 3 weeks by using the same modality and instrument. Any subject demonstrating any of the above manifestations of cardiotoxicity or >10% decrease in ejection fraction based on scans will be discontinued from the study. Between the Day 18 and Day 28 visits or at the the End of Treatment visit (if the subject is prematurely terminated), a final MUGA or ECHO scan or an ECHO strain evaluation will be conducted by using the same modality and instrument.

3.3.2 Myalgia – Adverse Event Workup

If a subject develops study drug-related \geq Grade 3 myalgia on study, total creatine phosphokinase and creatine phosphokinase isoenzyme measurements should be performed. Appropriate treatment with analgesics should also be initiated.

3.4 Criteria for Dose-Limiting Toxicity

A DLT is defined as any of the following clinically significant AEs or laboratory abnormalities that occur during the DLT evaluation period except those that are clearly and incontrovertibly due to extraneous causes, including disease progression, underlying disease, concurrent illness or concomitant medications. The DLT evaluation period is defined as the first day of treatment (Day 1) until Day 28. DLT observation periods for safety monitoring in expansion cohorts will be as above. The severity of AEs will be graded according to the NCI CTCAE v5.

Any Grade ≥ 3 nonhematologic or extramedullary toxicity with the following exceptions:

- Anorexia or fatigue;
- Grade 3 nausea and/or vomiting if not requiring tube feeding or total parenteral nutrition or diarrhea if not requiring or prolonging hospitalization that can be managed to Grade ≤ 2 with standard antiemetic or antidiarrheal medications used at prescribed dose within 7 days of onset;
- Grade 3 mucositis that resolves to Grade ≤ 2 within 7 days of onset;
- Grade 3 fever with neutropenia, with or without infection; or
- Grade 3 infection.

Any subject demonstrating the defining criteria for Hy's Law ([Appendix D](#)) will be discontinued from the study, and this will be considered a DLT.

Subjects who do not achieve a remission of leukemia will not be evaluable for hematological toxicity.

3.5 Evaluation of Efficacy

3.5.1 Bone Marrow Evaluation

Bone marrow aspirate (a biopsy if there are no spicules present) 15 to 35 days after the start of therapy will be performed. If cytogenetics were initially abnormal, include cytogenetics as part of the remission documentation.

3.6 Premedications and Prophylactic Treatments

3.6.1 Tumor Lysis Syndrome Prophylaxis

All subjects will receive tumor lysis syndrome prophylaxis as per institutional guidelines or as per published information ([Jones et al. 2015](#); [Coiffier et al. 2010](#)).

3.6.2 Allergic Reactions

Antiallergic premedication with an antihistamine (e.g., diphenhydramine at a dose of 50 mg administered intravenously) must be administered before each dose of liposomal annamycin.

Subjects who develop allergic reactions must have their infusions stopped and be treated with corticosteroids and/or diphenhydramine and other supportive measures as deemed appropriate by the Investigator on the basis of institutional standards of care. After the reaction has completely resolved, the infusion can be restarted at 25% of the original rate and slowly increased to 50% of the original rate. For subjects who experience an allergic reaction, prophylaxis with corticosteroids, as well as an antihistamine administered intravenously, will be required for all subsequent infusions. If any subjects experience an anaphylactic reaction to therapy, they will be permanently discontinued from the study.

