4. ECG

6.3 On-Study Evaluations

6.3.1 Study Drug Administration

Dosing will be in the morning at approximately the same time each day. Subjects will be treated with a daily 2-hour intravenous infusion of liposomal annamycin for 3 consecutive days. Prophylaxis as described in [Section 3.6](#) will be administered. Antiallergic premedication with diphenhydramine at a dose of 50 mg administered intravenously must be administered before each dose of liposomal annamycin. During each period of study drug administration subjects must be observed for at least 4 to 6 hours following daily liposomal annamycin administration. The following evaluations will be conducted during the 3 days of liposomal annamycin administration (Days 1 to 3):

1. Physical examination including weight, vital signs, and oral examination on Days 2 and 3
2. Blood samples for pharmacokinetic analysis collected at predose and at 0.25, 0.5, 1, 2, 4, 8, and 24 hours after the start of liposomal annamycin infusion on Day 1 and Day 3 for 3 subjects at each dose and 6 subjects at the RP2D who complete the 3 days of dosing
3. Blood samples for cardiac biomarkers (troponin-I and troponin-T) collected at predose, at the end of infusion on Day 3, and on Day 21
4. ECG monitoring at predose and at 4 hours and 24 hours after the start of liposomal annamycin infusion on Day 1, Day 2, and Day 3 for all subjects at each dose and 6 subjects on Day 1 and Day 3 only at the RP2D who complete the 3 days of dosing, coinciding with pharmacokinetic (PK) evaluations
5. Monitoring of adverse events and review of concomitant medications and concurrent illnesses (treatment-emergent or worsening illness must be recorded as an adverse event). Evaluation of blood chemistries and blood counts daily. Over the 3 days of initial dosing, if any toxicity occurs, including blood count abnormalities, dosing should be interrupted until resolution, with rechallenge at a 25% lower dose, based on guidelines in [Sections 3.3](#) and [3.4](#). If any DLT is encountered (as defined in [Sections 3.3](#) and [3.4](#)) including any severe or life-threatening event, the subject should be discontinued from the study. These specific events include (but are not limited to) development of an anaphylactic reaction during or after the infusion or clinical or radiological evidence of left ventricular dysfunction with dyspnea and pulmonary rales, cardiomegaly, or signs of pulmonary hypertension on chest x-ray.
6. Concomitant medications

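### Section 3.6.2 allows the infusion to restart after any allergic reaction short of anaphylaxis, without setting aside the Grade 3 or higher reactions for which Sections 3.3, 3.4 and 6.3.1 discontinue the subject

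*Combined protocol and SAP*

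**What the plan says.** **Section 3.6.2 (Allergic Reactions).** Antihistamine premedication is mandatory before each dose. If a reaction occurs, the infusion is stopped and the subject treated. Then, of the infusion rate: "After the reaction has completely resolved, the infusion can be restarted at 25% of the original rate and slowly increased to 50% of the original". Corticosteroid plus intravenous antihistamine prophylaxis "will be required for all subsequent infusions", so further dosing is contemplated. There is one exception: "If any subjects experience an anaphylactic reaction to therapy, they will be permanently discontinued from the study". No grade is mentioned, and neither Section 3.3 nor Section 3.4 is cited.

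**Section 3.4 (DLT criteria).** From Day 1 to Day 28 the nonhematologic criterion is "Any Grade ≥ 3 nonhematologic or extramedullary toxicity with the following exceptions". The five bullets that follow cover:
- anorexia or fatigue;
- certain Grade 3 nausea, vomiting or diarrhea;
- Grade 3 mucositis that improves within 7 days;
- Grade 3 fever with neutropenia;
- Grade 3 infection.

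Events plainly due to extraneous causes are also excluded.

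**Section 3.3 (Safety Considerations).** For a DLT, or any severe or life-threatening event in the first 3 days, "dosing should be stopped and the subject should be permanently discontinued from the study". Its list of severe events is expressly not exhaustive; anaphylaxis is on it.

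**Section 6.3.1, item 5.** This repeats discontinuation for a DLT or severe event. It also says that toxicity during the three dosing days leads to interruption and rechallenge at a dose reduced by 25%, by reference to Sections 3.3 and 3.4.

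**The concern.** Two parts of the protocol govern what happens next after the same event. Section 3.6.2 is where a site would look when a subject reacts during an infusion. Read alone, it allows the infusion to resume after every resolved reaction except anaphylaxis. The stopping rule in Section 3.3 removes some of those subjects permanently. The protocol does not say which section takes precedence.

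The first thing at stake is re-exposure of a subject whom the stopping rule would discontinue. The second is reporting: an event handled as a routine infusion reaction may not be put forward as a possible DLT. In cohorts of 3 to 6, a DLT that goes unreported can matter.

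**Working it through.** No arithmetic underlies the point, and the plan states no figure to reproduce. The check follows one event through the sections: a study-drug-related allergic reaction that is not anaphylaxis, is Grade 3, occurs on Day 1, 2 or 3, and resolves completely after treatment.

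| Section | What it gives for this event |
|---|---|
| 3.6.2 | Restart at a reduced rate is allowed; later infusions are foreseen with prophylaxis |
| 3.4 | DLT: Grade 3, nonhematologic, within Days 1 to 28, 0 of 5 exceptions apply, cause not extraneous |
| 3.3 | Dosing stops and the subject is permanently discontinued |
| 6.3.1, item 5 | Discontinuation, as a DLT or severe event |

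**Boundaries.**
- Grade 1 or 2 reaction: the nonhematologic criterion in Section 3.4 is not met, so this conflict does not arise.
- Anaphylaxis: Sections 3.3, 3.6.2 and 6.3.1 agree on discontinuation.
- Grade 3 or higher, not anaphylaxis: Section 3.6.2 leaves open a restart that the other three sections rule out.

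**Timing.** All three planned infusions fall on Days 1 to 3, so a reaction during an infusion always falls inside the Section 3.3 window. With 3 planned infusions, the number still to come after a reaction on Day d is 3 − d: two after Day 1, one after Day 2, none after Day 3. The rest of the interrupted infusion comes on top in each case.

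**Does the DLT wording elsewhere remove the overlap?** Section 3.1 and the synopsis describe a DLT more narrowly, as drug-related Grade 3 or higher toxicity that cannot be reversed or medically managed. A treated and resolved reaction might seem to escape. But Section 3.1 sends the reader to Section 3.4 for the full definition, and Section 3.4 has no such qualifier for this event. Section 3.3 also discontinues for any severe event, whether or not it is a DLT. It does not tie the word severe to a grade, though exclusion criterion 9 equates severe with Grade 3 or higher for mucositis.

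**Secondary point, Section 6.3.1.** The 25% dose reduction is worded to cover toxicity in general during dosing, while Section 3.6.2 changes the infusion rate and says nothing of dose. Section 6.3.1 refers to Sections 3.3 and 3.4 for guidance, and Section 3.3 ties the 25% reduction to creatinine and liver tests. Whether it is meant to reach allergic reactions is unclear.

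**The case against.** The strongest reply is that both rules can be obeyed together. Section 3.6.2 is permissive: it says the infusion may be resumed, not that it must be. A site that discontinues a Grade 3 reaction under Section 3.3 breaches nothing in Section 3.6.2, which can be read as guidance for milder reactions. This stands as far as it goes. A reader might infer that the sections give strictly opposite instructions, and the text does not support that. What it leaves standing is that Section 3.6.2 singles out anaphylaxis as its only reason to discontinue, so a site reading it alone would reasonably take every other reaction as eligible for restart.

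A reader might also infer that DLT status itself is in dispute. It is not. Section 3.6.2 says nothing about DLTs, Section 3.4 already includes the event because it is not excepted, and the synopsis and Section 8.2 give designation of DLTs to the SRC. The remaining risk is narrower: the SRC can designate only what is reported to it, and its later designation does not settle the immediate decision to resume or stop.

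It is tempting, too, to call the 25% reduction a firm second contradiction. The reference in Section 6.3.1 to Sections 3.3 and 3.4 prevents that; the wording is unclear, not contradictory.

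Finally, a slowed infusion might be thought to spoil the timed PK and ECG records. That would follow from any slowed infusion and has nothing to do with this inconsistency. Footnote k of Appendix A already allows latitude in PK sampling times.

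**Conclusion.** The point holds as an unreconciled overlap between the reaction-management text and a stopping rule. It is limited to study-drug-related, non-anaphylactic allergic reactions of Grade 3 or higher during the three dosing days. For those events, a site following Section 3.6.2 as written could re-dose a subject whom Sections 3.3 and 6.3.1 discontinue, and might not report the event for DLT designation.

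The size per subject is the rest of one infusion plus up to two more. The size across the trial cannot be given, because the documents report no rate of such reactions; mandatory premedication shows only that allergic reactions are foreseen. If one such event did go unreported, the 3+3 count could read 0 of 3 instead of 1 of 3 (escalate instead of expanding to 6), or 1 of 6 instead of 2 of 6 (tolerated instead of nontolerated). That is true of any missed DLT and does not show that Section 3.6.2 would cause one.

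The conclusion assumes that CTCAE v5, which is not reproduced in the documents, leaves room for a Grade 3 allergic reaction that is not anaphylaxis. The matter should be corrected because it concerns stopping and re-exposure, and wording alone can settle it.

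**What to change.** Reconcile Section 3.6.2 with Sections 3.3, 3.4 and 6.3.1. In Section 3.6.2, state which allergic reactions the restart and later infusions cover and which fall under Sections 3.3 and 3.4, and cite those sections. Where the line lies, and which rule governs, is for the clinical team. Add that a reaction meeting the Section 3.4 criteria is reported for DLT designation by the SRC however it was managed at the bedside.

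As a smaller change, add a clause to item 5 of Section 6.3.1 saying whether the rechallenge at a dose reduced by 25% applies to reactions managed under Section 3.6.2.

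The cost is a few sentences in a protocol amendment. No procedure, visit, sample size or analysis needs to change.

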3.6.3 Oral Prophylaxis for Mucositis

3.6.3.1 Mouthwash

Subjects will receive mouthwash as per the institution's guidelines and practices.

3.6.3.2 Palifermin (Kepivance)

The use of Kepivance should be considered if institutional guidelines and the Investigator recommend it, but is not required. Kepivance is indicated as supportive care for preparative regimens predicted to result in \geq Grade 3 mucositis in the majority of subjects. The recommended dose of Kepivance is 60 $\mu\text{g}/\text{kg}/\text{day}$ administered as an intravenous bolus injection for 3 consecutive days before and 3 consecutive days after myelotoxic therapy for a total of 6 doses.

3.6.3.3 Oral Cryotherapy

Subjects must receive oral cryotherapy (ice chips) during liposomal amphotericin administration, utilize the recommended administration at 5 minutes prior to treatment, and continue for 2 to 6 hours thereafter ([Lilleby et al. 2006](#)).

4. ELIGIBILITY CRITERIA

Subjects were diagnosed with AML refractory to or relapsed after standard induction therapy. All subjects must meet the inclusion and exclusion criteria listed below to be eligible for enrollment. Subjects with central nervous system (CNS) involvement will be eligible for this study. They will receive CNS therapy as per standard of care.

4.1 Inclusion Criteria

A subject may be included in this study if he/she meets all of the following criteria:

1. A pathologically confirmed diagnosis of AML by World Health Organization classification
2. AML that is refractory to or relapsed after standard induction therapy
3. Age ≥ 18 years at the time of signing informed consent
4. No chemotherapy, radiation, or major surgery within 2 weeks prior to first dose of study drug and/or recovered from the toxic side effects of that therapy unless treatment is indicated due to progressive disease
5. No investigational therapy within 4 weeks of the first dose of study drug
6. Eastern Cooperative Oncology Group (ECOG) performance status 0 to 2

7. Adequate laboratory results including the following:
 - a. Bilirubin ≤ 1.5 times the upper limit of normal unless due to Gilbert Syndrome.
 - b. Serum glutamic-oxaloacetic transaminase (SGOT), serum glutamic-pyruvic transaminase (SGPT), and alkaline phosphatase < 3 times the upper limit of normal unless due to organ involvement.
 - c. Adequate renal function (The Cockcroft-Gault equation will be used to estimate creatinine clearance. This equation is as follows: Creatinine clearance in milliliters per minute = $[140 - \text{age}] \times \text{body weight [kg]} / 72 \times \text{plasma creatinine [mg/dL]}$, multiplied by 0.85 for women. By using this equation, adequate renal function will be deemed to be a creatinine clearance of greater than 60 mL/minute.)
8. Prior anthracycline cumulative dose (see [Table 2](#) and [Appendix E](#)) $< 551 \text{ mg/m}^2$ or the daunorubicin equivalent, which is the recommended noncardiotoxic level. This will be calculated as follows:
 - a. Determination of prior exposure will be based on total milligrams per meter squared of prior anthracycline therapy (see [Appendix C](#) for commonly used chemotherapy regimens incorporating anthracyclines).
 - b. Potential cardioprotective measures for anthracycline drugs and analogues by limitation of cumulative doses are demonstrated by the conversion factors in [Table 2](#).
 - c. The maximal allowance will be calculated as a daunorubicin equivalent added to the anticipated exposure to liposomal irinotecan with the maximal exposure of anthracyclines capped at 550.9 mg/m^2 ([Appendix E](#)).
 - d. Exposure to irinotecan projected for subjects enrolled in a given cohort in this study will be assessed on the basis of prior total exposure added to the anticipated designated cohort dose level (up to 120 mg/m^2 , which, after 3 doses, represents a cumulative exposure of $< 551 \text{ mg/m}^2$ daunorubicin equivalents).
9. Subject can understand and sign the informed consent document, can communicate with the Investigator, and can understand and comply with the requirements of the protocol.
10. Women of childbearing potential must have a negative serum or urine pregnancy test.
11. All men and women must agree to practice effective contraception during the entire study period and after discontinuing study drug, unless documentation of infertility exists.
 - a. Sexually active, fertile women must use 2 effective forms of contraception (abstinence, intrauterine device, oral contraceptive, or double barrier device) from the time of informed consent and until at least 6 months after discontinuing study drug.
 - b. Sexually active men and their sexual partners must use effective contraceptive methods from the time of subject informed consent and until at least 3 months after discontinuing study drug.

